#### 9.4.4.3 *Analysis of the count data obtained by passive case detection*

The incidence data obtained from routine passive case detection in health facilities and through CHV in villages will be analysed using multi-level variance compartments models, constructed on a generalized linear model framework with a Poisson likelihood and a log link function. Random intercepts will be included for each study cluster, and the study arm will be included as a fixed effect. Denominator data to obtain person time for each cluster will be based on the enumeration data obtained from the census. Model results will be presented as incidence rates and incidence rate ratios, their associated 95% confidence intervals and p-value. Similar to the analysis of primary outcome, each count outcomes will also be checked for the distributional assumption that the mean and variance of the outcome are similar after conditioning on cluster (e.g. are the within-cluster mean and variance similar). If the variance is substantially larger, a negative binomial likelihood will be considered.

#### 9.4.5 **Analysis of entomological data**

Mosquito densities will be analysed by Poisson or negative binomial regression using generalized estimating equations to adjust for correlated observations at the cluster level. Separate models will be done for each species where adequate numbers have been collected. All models will assume an auto-regressive correlation structure where the degree of correlation decreases with increasing time between collections. Models will include potential confounders such as the use of LLINs, recent house spraying, the presence of open eaves, and climatic factors. Logistic regression models will be used to compare the impact of ATSBs on binary outcomes such as the sporozoite rates, parity rates, the proportion of mosquitoes with three or more ovarian dilatations, or the proportion of outdoor biting. The logistic regression models will adjust for correlated observations at the cluster level using assuming an auto-regressive correlation structure.

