### 6.3.8 Entomological monitoring

#### 6.3.8.1 *Monthly/quarterly mosquito catches*

Entomological data will be collected on a monthly basis from 10-12 households in each of 24 randomly selected study clusters (12 intervention and 12 control; total= 240-288 houses per month). Collection of monthly mosquito catches will use UV light traps. Human landing catches will be performed quarterly in 4 houses in each of 12 randomly selected clusters (6 control and 6 intervention clusters; total = 48 houses per quarter).

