### 7.8.3 Entomological monitoring

Twelve intervention clusters and 12 control clusters will be selected for entomological monitoring. Based on previous field research in Mali, large reductions in mosquito density are anticipated, up to 90% (although density reductions may be dependent on the season due to seasonal fluctuations in abundance). A minimum reduction in density of 50% was used for sample size calculation.

Ten 10 entomological collections per cluster per month are required to detect a 50% reduction in mosquito densities per CDC UV light trap (two-sided alpha=0.05, power=80%, ICC=0.38, 24 clusters

[12 per arm]). For the impact of ATSBs on parity or sporozoite rates, all unfed mosquitoes captured alive will be used to estimate parity rates. All Anopheles mosquitoes collected during the study will be subjected to ELISA to estimate sporozoite infection rates.

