##### 9.1.5.1 *UV light traps*

1. Twelve intervention area and 12 control area clusters will be randomly selected for entomological monitoring using UV Light traps.
2. Entomological field assistants will receive training in the study methods and procedures for mosquito collections.
3. Informed consent will be administered to the head of household
4. UV light trap collections will be conducted monthly for the duration of the trial. The household sampling frame generated during the census will be used to select a random sample of 10-12 households per cluster.
5. Collections from clusters will be completed in pairs: one intervention and one control cluster pair. If feasible, collections from all 10-12 households in each of the 2 clusters will be completed in one night. If this is not feasible, collections will be completed over two nights from 5-6 households per cluster per night.
6. In each selected household, a UV light trap will be hung at the foot of a bed or sleeping space by the entomology field team between 1700-1800HRS in the evening. The UVLT should be set next to a bed or sleeping space with a net hanging over it. The house owners will be instructed not to touch it until removed by the team the next morning
7. An additional light trap will be set up outdoors
8. In the morning, the entomology field assistants will visit the household, ensure the UVLT is still running and then carefully remove the collection cup to ensure no mosquitoes escape. Mosquitoes will be returned to the KEMRI CGHR laboratory in Kisian or a field laboratory, where mosquitoes will be sorted and processed for further analyses.

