#### 9.1.5.2 *Human landing catches*

1. Six clusters not included in the monthly UVLT sampling will be randomly selected from each arm, and within each cluster, four households will be purposively selected for quarterly indoor and outdoor mosquito collections using human landing catches. Each household will participate in this collection for two nights.
2. Selected households will be visited in advance of the collection night and provided information about the study. Informed consent will be sought from the head of the household or his/her representative.
3. A team of 6 collectors will be consented per house. They will be divided into pairs, and each pair will work up to a 6-hour shift during the night. Collections will begin at 5 pm in the evening and continue through 11 am the following morning.
4. Collectors will work for 45 minutes each hour and then take a 15-minute break to rest, take food if necessary and prepare for the next hour of collection. Each pair of collectors will work for 6 hours before a new shift will take over.
5. Prior to the HLC, collectors will be trained to properly aspirate mosquitoes, ideally before they are bitten, and will have ample time during training to practice the technique so as to minimize bites during collections.
6. The collectors will sit in fixed spots, one inside the house and one outside at least 5m away from the house. They will then expose their lower legs, and using a torch (flashlight) and a mouth aspirator, they will collect mosquitoes that land on their lower legs. Collected mosquitoes will be placed in individually labelled paper cups with a separate cup for each hour of indoor collection and outdoor collections.
7. Mosquitoes will be returned to the KEMRI CGHR laboratory in Kisian or a field laboratory in the study area where mosquitoes will be sorted and processed for further analyses.

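### The auto-regressive GEE prescribed for mosquito densities does not fit the trapping design, so with 12 or 6 clusters per arm the tests are too liberal unless a small-sample correction is stated

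*Protocol*

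**What the plan says.** Protocol section 9.4.5 fixes the method for densities: "Mosquito densities will be analysed by Poisson or negative binomial regression using generalized estimating equations to adjust for correlated observations at the cluster level". It then fixes the correlation: "All models will assume an auto-regressive correlation structure where the degree of correlation decreases with increasing time between collections". Sporozoite, parity, ovarian-dilatation and outdoor-biting outcomes get logistic regression: "The logistic regression models will adjust for correlated observations at the cluster level using assuming an auto-regressive correlation structure". GEE is named only for densities.

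The cluster numbers are small. Section 9.1.5.1: "Twelve intervention area and 12 control area clusters will be randomly selected for entomological monitoring using UV Light traps". Each month 10–12 households per cluster are trapped, in one night if feasible and otherwise over two. Section 6.3.8.1: "Human landing catches will be performed quarterly in 4 houses in each of 12 randomly selected clusters (6 control and 6 intervention clusters". Section 9.1.5.2 keeps these apart from the trap clusters: "Six clusters not included in the monthly UVLT sampling will be randomly selected from each arm".

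Section 7.8.3 plans the light-trap sample at two-sided 5%, 80% power and an ICC of 0.38. Section 9.4.2.3 says that all analyses will obtain standard errors from a model with a random cluster intercept, which is not GEE. The protocol does not say whether the GEE standard errors are robust or model-based, whether the reference distribution is normal or t, or whether a small-sample correction applies.

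**The concern.** Two features of the prescribed structure do not match the sampling. Households in one cluster trapped on the same night have no time order, so an auto-regressive sequence among them has no meaning. A cluster that is persistently wetter, or closer to breeding sites, stays correlated with itself across all months, yet an auto-regressive structure forces that correlation towards zero. The working correlation is therefore wrong in a predictable direction, and the inference is protected only by the robust (sandwich) standard error.

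That estimator is biased downward when clusters are few, and 24 or 12 in total is few. Entomological results are the mechanistic evidence beside the primary result, and the study results go to the WHO advisory group. They include several outcomes, density models are fitted by species, and section 9.4.2.1.3 makes no multiplicity adjustment. Standard errors that are too small would give too many false findings of an effect on the vectors.

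**Working it through.** **Inputs from the protocol.** K = 12 clusters per arm (traps) and K = 6 (landing catches); two-sided 5%; ICC 0.38; 10 collections per cluster per month; 50% reduction; 80% power.

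**Inputs not in the protocol.** Mean density, its variance, and the between-cluster coefficient of variation (CV). These are assumed below and varied.

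**1. The plan's own figure (10 collections per cluster per month).** Design effect = 1 + (10 − 1) × 0.38 = 4.42. Effective collections per arm = 120 / 4.42 = 27.1. With a normal approximation, 80% power for a halving then requires a per-collection CV of about 0.83 (equal CV in both arms), or 0.66 (equal SD). The protocol states no such value, so the 10 can be neither confirmed nor refuted. Taking 0.83, the implied between-cluster CV is √0.38 × 0.83 = 0.51, used below as the central case.

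**2. Closed form, uncorrected sandwich with a normal reference.** For normal cluster summaries the error rate is P(|t(2K−2)| > 1.96 × √((K−1)/K)).
- K = 12: the threshold is 1.96 × √(11/12) = 1.877 on 22 df, giving 7.4%.
- K = 6: the threshold is 1.96 × √(5/6) = 1.789 on 10 df, giving 10.4%.

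**3. Simulation under the null, uncorrected sandwich with a normal reference.**

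| Setting | 12 per arm | 6 per arm |
|---|---|---|
| Over-dispersed counts, CV 0.51 | 7.8–8.6% | 11.6–12.6% |
| CV 0.3–0.8 | 7.7–9.9% | 10.9–14.3% |
| CV 1.0–1.3 | 9.7–11.9% | 14.4–17.7% |
| AR(1)-weighted estimator | about 8–11% | about 12–16% |
| AR(1) GEE fitted to cluster-month means, CV 0.51 | 9.2% (500 runs) | 9.0% (700 runs) |

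The Monte Carlo standard error in the last row is about 1 point. Poisson estimating equations with an independence working correlation, lognormal cluster effects and monthly effects ran higher: 8.9–14.2% and 13.2–20.8%, with or without household covariates. No binary outcome was simulated.

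**4. Model-based standard errors instead.** Take 24 months × 10 houses, total ICC 0.38, 25–100% of the cluster variance lasting and the rest independent by month. In a linear approximation, AR(1) on cluster-month means gives standard errors 0.47–0.68 of the true value. The error rate is 2 × (1 − Φ(1.96 × ratio)): 36% at 0.47 and 18% at 0.68.

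**5. After correction.** Multiplying the variance by K/(K−1) and using t on 2K−2 df gives 5.0% in the closed form. Simulated at CV 0.4–0.56 it gives 5.3–6.1% (12 per arm) and 5.4–6.4% (6 per arm); the AR(1)-weighted estimator gives about 5–8%. The repair weakens at high variation: with 6 per arm and CV 1.3 the rate is still 9.2–9.6%. In the AR(1) GEE runs, a bias-reduced variance with a t reference gave 5.6% (12 per arm) and 2.6% (6 per arm), so over-correction is also possible with 6.

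**6. Cost in power.** If the planned 80% used a normal critical value (non-centrality 1.96 + 0.84 = 2.80), replacing it by t(22) gives about 76%.

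**The case against.** The strongest objection is that the variance estimator, the reference distribution and any correction are details that a protocol may leave to the statistical analysis plan. This protocol defers to one in several places. GEE with 24 clusters is valid once corrected, and section 9.4.5 does not forbid a correction. This stands against any claim that the trial has chosen uncorrected tests. A reader might infer from section 9.4.5 that these tests do run at inflated error; the documents show only what would follow without a correction. The objection does not dispose of the point, because the auto-regressive structure is stated, not deferred, and it is what makes the result hinge on the variance estimator.

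A second objection is that section 9.4.2.3 already prescribes a random cluster intercept, so sandwich errors need not arise. That is a conflict between two sections and not an answer: 9.4.5 is the specific instruction and it names GEE.

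Third, the rates depend on assumed variation, and the direct AR(1) GEE run with 6 clusters per arm gave 9.0%, below the other results for that design. This is fair and is why a range is given. That run still exceeds 5%, so the auto-regressive analysis does not escape the problem.

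Fourth, the outcomes are secondary. That is correct. The effect tied to a WHO recommendation is a 30% reduction in clinical malaria, assessed on 40 clusters per arm.

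**Conclusion.** The point holds in conditional form. The prescribed working correlation does not suit same-night collections or lasting cluster differences, so the density comparisons rely on the robust standard error. Without a small-sample correction and with a normal reference, nominal 5% tests would run at about 7–11% with 12 clusters per arm and 10–16% with 6. They would run higher if between-cluster variation is large (CV of 1 or more), and model-based errors would be worse (18–36% under the assumptions shown). The lower ends are the closed form; the rest depends on a between-cluster variation that the protocol does not report.

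Two wider readings are not supported. The binary outcomes share the structure and the cluster counts, so the same concern applies, but GEE is not named for them and no error rate was computed. Nothing here touches the primary outcome, which is analysed by a different model on all 80 clusters.

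**What to change.** Reconcile section 9.4.5 with section 9.4.2.3 so that one method governs the entomology comparisons. Then state in 9.4.5 that:

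- comparisons use cluster-robust standard errors with a named small-sample correction;
- the reference is t on clusters minus 2 degrees of freedom (22 for light traps, 10 for landing catches), fewer if cluster-level covariates such as climate enter the model;
- the auto-regressive structure is either replaced or justified for collections made on the same night.

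A cluster-summary analysis is an acceptable alternative and is simple to defend with 6 clusters per arm. The chosen correction should be checked by simulation once baseline data give the between-cluster variation, because the simple K/(K−1) version is not enough when variation is high.

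The change is to wording only. Relative to uncorrected normal intervals on the log scale, widths grow by (2.074 / 1.960) × √(12/11) = 1.11 for light traps and (2.228 / 1.960) × √(6/5) = 1.25 for landing catches. Light-trap power falls to about 76% from 80% if the original calculation used a normal critical value.

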To determine if ATSB deployment plus universal LLIN coverage compared to universal LLIN coverage alone reduces malaria transmission or affects insecticide resistance	
 
Entomological outcomes including malaria vector densities, the proportion of females older than three gonotrophic cycles, sporozoite rate, EIR and markers of insecticide resistance
 
Antibodies against merozoite surface protein-1 (MSP-1), circumsporozoite proteins (CSP) and other malaria antigens
 
Molecular measurements including, but not limited to, 24-single-nucleotide polymorphisms (24-SNP) barcodes for the complexity of infection
 
Mosquito salivary antigens for biting rates
 

5.2.2 Safety	
Assess the safety of ATSBs on humans	
 
Adverse events associated with misuse or loss of ATSBs.
 

Assess the safety of ATSBs on non-target insects	
 
Continued entomological monitoring of non-target insect populations
 

5.2.3 Ethnographic evaluation	
To understand the acceptability and potential factors that influence ATSB coverage	
 
The proportion of ATSBs that have been moved/removed
 
The proportion of household heads who perceive ATSBs as safe and effective
 

Assess the acceptability of ATSBs by communities and other stakeholders	
 
Identification of potential barriers to uptake and consistent ATSB coverage,
 
Assessment of the impact of ATSBs on the coverage and use of existing malaria control interventions (e.g. LLIN, IRS, treatment-seeking behaviour)
 

5.2.4 Health economics	
Estimate the cost-effectiveness of deploying ATSBs for malaria control.	
 
Incremental cost-effectiveness of ATSB above the standard of care measured through costing of intervention and efficacy outcomes
 

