#### 7.6.3 **Other malaria control interventions**

Community-case management of malaria by community health volunteers is an active intervention promoted by the Ministry of Health in this area. In this strategy, community health volunteers test and treat participants encountered in the households who complain of symptoms compatible with

malaria. Additionally, in September 2019, the Kenya Ministry of Health began a phased implementation of GSK's Mosquirix vaccine in children aged 5-17 months of age. Rarieda sub-county was chosen as an initial vaccinating sub-County, whereas Alego-Usonga was not. To control for the impact of RTS,S/AS01 on our study outcomes, we will ensure a balance of clusters between arms in Rarieda and Alego-Usonga sub-Counties. Additionally, we will record the vaccination status of all children <5 years of age from the maternal-child booklet or from vaccination cards. Where available, we will take a photograph of the child's vaccination records. Where not available, we will use maternal recall. The Kenya Division of National Malaria Program (DNMP) does not currently have plans to perform IRS in Siaya County during the trial period. Should IRS be implemented in the trial area during the trial, the study team will monitor timing and coverage of the campaign at a household and cluster level but will not be responsible for regulating or "topping up" IRS should DNMP initiate spraying in the area.

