## 8.2 BLINDING

Allocation of study arms will not be blinded to the participants, the deliverers of the intervention, or the main investigators. Sham ATSBs will not be deployed in control areas because it is logistically not feasible to produce the number of ATSB stations needed for both intervention and control arm. The potential for bias among operator-dependent mosquito catches (indoor and outdoor aspirations) will be minimized using a standardized protocol. Additionally, the potential for bias in mosquito catches using CDC light traps is very low. The potential for changes in human behaviour affecting malaria control intervention coverage, namely LLIN use, will be minimized through comprehensive community engagement and communications. LLIN use will be promoted in intervention and control areas. Additionally, study teams will monitor LLIN use in intervention and control areas to document changes throughout the life of the study. Laboratory processing of mosquito and human blood specimens will be blinded.

To further minimize bias, we will use an objective primary outcome measure and mask all laboratory staff to the treatment assignment of individual participants. The trial statistician will also be blinded regarding the allocation arm when the statistical analysis plan is developed and the analytical syntax is written, which will be validated and completed using dummy randomization codes. The actual

allocation will only be provided to the study team after locking the database and approval of the statistical analysis plan by the independent DSMB before they review any trial results.

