### 9.2.4 Entomological monitoring

Field data will be recorded using electronic data capture forms on mobile phones or tablets. This will include details on the house structure (e.g., roof type, wall type, open or closed eaves), presence and use of LLINs, the timing of any IRS application within the last 12 months, and other factors that may affect mosquito density (e.g., cooking in the house, use of mosquito coils, presence of animals). Laboratory data will be entered using a standardized data entry form either directly on a PC or a

tablet. Data will be imported into Microsoft Access, and data merging, cleaning, and analysis will be done using a standard statistical software package such as SAS, Stata or R.

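### The mosquito-density models in 9.4.5 adjust for LLIN use recorded after randomisation, which is a possible mediator of ATSB and not a confounder, so they do not estimate the total effect

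*Protocol*

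**What the plan says.** Section 9.4.5 analyses mosquito densities by Poisson or negative binomial regression with generalized estimating equations, and then states: "Models will include potential confounders such as the use of LLINs, recent house spraying, the presence of open eaves, and climatic factors". It describes no density comparison without these covariates. The logistic models for sporozoite rate, parity and similar binary outcomes follow in the same section and are described with an adjustment for clustering but no covariate list.

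On timing, section 9.2.4 places these items in the entomological field record: "presence and use of LLINs, the timing of any IRS application within the last 12 months". Section 9.1.5.1 adds: "UV light trap collections will be conducted monthly for the duration of the trial".

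On what ATSB might change, Table 1 (section 5.2.3) lists as an endpoint: "Assessment of the impact of ATSBs on the coverage and use of existing malaria control interventions", with LLIN and IRS among its examples. Section 8.2, on the absence of blinding, says: "The potential for changes in human behaviour affecting malaria control intervention coverage, namely LLIN use, will be minimized through comprehensive community engagement and communications". It also commits the study to monitoring LLIN use in both arms.

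The entomological objective in Table 1 (section 5.2.1) is an arm comparison: ATSB plus universal LLIN coverage against universal LLIN coverage alone.

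**The concern.** Clusters are allocated at random, so net use observed during follow-up cannot confound the comparison of arms. Chance imbalance at baseline is a separate matter. Section 8.1 already lists baseline bednet use as a candidate restriction factor, and a baseline value can also be adjusted for without difficulty.

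Concurrent net use may itself respond to the intervention. Households with bait stations on the wall might use nets less, or community engagement might lead them to use nets more. Conditioning on net use removes whatever part of the ATSB effect on density runs through it. If net use falls in the ATSB arm and nets lower the measured density, the adjusted model gives a larger reduction than the one the deployment achieves. If net use rises, the error goes the other way.

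The entomological results are meant to be read beside the clinical ones, which target the total effect. A density ratio that holds net use fixed answers a different question, and 9.4.5 does not say so.

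**Working it through.** **Reading the sections together.** The point does not turn on a figure in the protocol, so there is none to reproduce first.

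1. Covariates in the density models: LLIN use, recent house spraying, open eaves, climate (9.4.5).
2. When LLIN use is recorded: at the entomological collections (9.2.4), monthly through the trial (9.1.5.1), hence after randomisation.
3. Whether ATSB may affect it: listed as an endpoint (5.2.3) and acknowledged as possible (8.2).
4. Comparison wanted: ATSB plus LLINs against LLINs alone (5.2.1).
5. Treatment of other outcomes: the primary analysis is crude (9.4.3.1). The models for survey prevalence and for passively detected cases specify study arm and cluster intercepts (9.4.4.2, 9.4.4.3). The covariables for adjusted analyses in Table 4 (9.4.3.3) include neither LLIN use nor spraying.

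From 2 and 3, LLIN use is a possible mediator. From 1 and 4, the density model conditions on it although the objective is the total effect. From 5, the density analysis is the exception within the plan.

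**Size.** The protocol gives neither a difference in net use between arms nor an effect of net use on trap density. The inputs below are therefore assumptions. With a log-link model, let p0 and p1 be the proportions using a net in control and ATSB, and r the density ratio with against without a net in use, taken as equal in both arms:

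Total ratio = adjusted ratio × (p1·r + 1 − p1) / (p0·r + 1 − p0)

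The adjusted ratio is set at 0.50, the 50% reduction used for the entomological sample size (7.8.3).

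With p0 = 0.80, p1 = 0.70, r = 0.5:
- numerator: 0.70 × 0.5 + 0.30 = 0.65
- denominator: 0.80 × 0.5 + 0.20 = 0.60
- factor: 0.65 / 0.60 = 1.083
- total ratio: 0.50 × 1.083 = 0.54, a 46% reduction where the adjusted model shows 50%

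Total ratio over a range, with p0 = 0.80 and adjusted ratio 0.50:

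| Net use in ATSB arm | r = 0.4 | r = 0.6 | r = 0.8 |
|---|---|---|---|
| 80% (no change) | 0.50 | 0.50 | 0.50 |
| 75% | 0.53 | 0.51 | 0.51 |
| 70% | 0.56 | 0.53 | 0.51 |
| 60% | 0.62 | 0.56 | 0.52 |

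**Against sampling error.** A design with 80% power at two-sided 5% for a ratio of 0.50 implies a standard error of the log ratio of about 0.693 / 2.80 = 0.25, so a 95% interval of roughly 0.31 to 0.81 around 0.50. The shift in the worked example is ln(1.083) = 0.08, about a third of one standard error. If the calculation in 7.8.3 describes a single month of collections, pooled data would be more precise and the shift relatively larger.

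**The case against.** Several points can fairly be made for the plan as written.

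- **Scope.** A reader might infer that every entomology model carries this adjustment. The text does not support that: the covariate sentence follows the density models, and the logistic models list no covariates. This limit stands.
- **Spraying.** A reader might give house spraying the same weight as nets. Section 7.6.3 says the national programme "does not currently have plans to perform IRS in Siaya County during the trial period", and nothing in the protocol shows how ATSB would alter programme spraying. If spraying occurred, it would be an outside source of imbalance across a small number of clusters, and adjusting for it would be defensible. IRS appears among the examples in the 5.2.3 endpoint, but this limb is weak.
- **Behaviour change is possible, not predicted.** Section 8.2 aims to minimise it, nets are promoted in both arms, and top-up nets are provided for (6.3.6, 7.6.2). This stands, and it is why the gap may be nil.
- **Trap placement.** Section 9.1.5.1 has the indoor trap set beside a sleeping space with a net hanging over it, and a second trap outdoors. This partly standardises net presence at the indoor trap, and an indoor net effect need not apply to the outdoor one. It reduces the likely size.
- **The cost is visible elsewhere.** LLIN use is monitored by arm, and the primary clinical analysis is crude, so any loss of net use would not go unseen in the trial. That is true, but the density ratio itself would still exclude it.
- **The objective names universal LLIN coverage in both arms,** so holding net use fixed has some logic. Coverage is not nightly use, however, and the objective is still stated as a comparison of arms.
- **A matter for the SAP.** The covariate list is illustrative and no crude model is ruled out. Even so, the protocol states what the density models will include and calls LLIN use a potential confounder, which is wrong for a randomised comparison.

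None of this makes concurrent LLIN use a confounder.

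**Conclusion.** The point holds for the mosquito-density models and chiefly for LLIN use. As 9.4.5 stands, the adjusted ratio targets an effect with net use held fixed and not the total effect of ATSB plus LLINs against LLINs alone.

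The size is conditional. It is nil if net use does not differ by arm. Falls of 5 to 20 percentage points in the ATSB arm from an assumed 80% would move a ratio of 0.50 to between 0.51 and 0.62, depending on the assumed net effect, and the central example gives 0.54. Trap placement makes the lower end more likely for the indoor traps.

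A reader might infer that the trial will overstate the ATSB effect on transmission. The documents do not support that. They give no evidence that net use will fall, the sporozoite and parity models are described without these covariates, and the primary clinical analysis is unadjusted. Open eaves and climate are not affected by the objection. These are secondary outcomes. The change is worth making because it settles which effect is being estimated before the data are seen, and it costs almost nothing.

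**What to change.** In 9.4.5, state that the main density comparison includes study arm only, or study arm with exogenous or baseline covariates: climate, house structure, and cluster net use from the baseline survey.

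Baseline density should be added only where it exists. Section 6.3.2 plans baseline entomology in 30 clusters. The main trial monitors 24 light-trap clusters and 12 different landing-catch clusters (9.1.5.1, 9.1.5.2), 24 + 12 = 36 in all, so at least six will have none. The protocol does not state how far the 30 overlap with the 24.

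Report the model with concurrent LLIN use and spraying as a supportive analysis, described as an effect with those factors held fixed, and drop the term confounder for them. Present LLIN use by arm beside it.

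The cost is a short edit to 9.4.5 and one further model run. It needs no new data and leaves the sample size and collection schedule unchanged.
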